9.6 Safety Analyses

9.6.1 Adverse Events

TEAEs will be classified into a standardized terminology using the MedDRA system organ classifications and preferred terms. Version 20.0 of MedDRA will be used as coding dictionary. The incidence of TEAEs will be summarized for the Safety Population.

A summary of TEAEs including the number of events reported, the annual rate and the number and percentage of subjects reporting the following will be presented:

- Any TEAE
- Any TEAE leading to death
- Any treatment-emergent SAE
- Any TEAE leading to premature discontinuation from the study
- Any SAE related to study medication

TEAEs are defined in Section 5.11. The annual rate will be derived as the number of events divided by the total exposure across all subjects in years.

A breakdown of the number and percentage of subjects reporting each TEAE with the corresponding number of events, categorized by body system and preferred term coded according to the MedDRA dictionary, will be presented. Note that subjects are only counted once within each body system or preferred term but subjects with multiple events of a specific type will be counted once for each occurrence in the number of events column.

A further tabulation of these data, categorized by relationship to study drug, will be presented. Subjects with multiple events within a particular body system or preferred term will be counted under the category of their most drug-related event within that body system or preferred term in column for the number of subjects. In the column for the number of events, multiple events of a specific type and relationship will be counted once for each occurrence. Relationship to study drug is categorized as not related (not related and unlikely on the CRF) and related (possible, probable and highly probable on the CRF). This will be repeated for TEAEs leading to premature discontinuation from the study.

TEAEs will also be presented by severity. For each system organ class and preferred term, subjects are included only once, at the maximum severity. In the column for the number of events, multiple events of a specific type and severity will be counted once for each occurrence.

All adverse events (including non-treatment-emergent events) recorded on the CRF will be listed. The following listings will be generated in the Screened Population:

- All AEs
- AEs leading to premature discontinuation from the study

9.6.2 Deaths and Serious Adverse Events

A tabulation of SAEs, categorized by relationship to study drug, will be presented. Subjects with multiple events within a particular body system or preferred term will be counted under the category of their most drug-related event within that body system or preferred term in column for the number of subjects. In the column for the number of events, multiple events of a specific type and relationship will be counted once for each occurrence. Relationship to study drug is categorized as not related (not related and unlikely on the CRF) and related (possible, probable and highly probable on the CRF).

The following listings will be generated including non-treatment emergent events in the Screened Population:

- All SAEs
- All AEs leading to death
- All SAEs related to treatment (includes SAEs where the relationship to study drug is possible, probable and highly probable)

9.6.3 Laboratory Data

Central laboratory data will be used for the tables and listings. The scheduled laboratory assessments will be included in the tables where data are available. If a specific parameter is missing at the scheduled assessment and there is an unscheduled assessment collected at the same visit where this parameter is not missing, then the value at the unscheduled assessment will be used in the table. Otherwise unscheduled assessments will not be included in the tables. Note that unscheduled pregnancy tests will be used in the assessment of pregnancies for the primary endpoint. The parameters listed in **Table 4** will be summarized. Separate outputs will be provided for hematology, serum chemistry and lipid profile.

Table 4: Laboratory Parameters

Hematology	
Hemoglobin	Mean cell volume
Hematocrit	White blood cell & Differential
Red blood cell count	Platelet count
Serum Chemistry	
Albumin	Total protein
Alanine aminotransferase (ALAT)	Serum creatinine
Aspartate aminotransferase (ASAT)	Sodium
Blood urea nitrogen	Potassium
Gamma glutamyl transferase (GGT)	Calcium
Glucose	Chloride
Glycated hemoglobin	Bicarbonate
Lactate dehydrogenase (LDH) 1 and LDH 2	Phosphorus
Total bilirubin	Choriogonadotropin Beta (Serum Pregnancy Test)
Estimated Glomerular Filtration Rate (eGFR)	
Lipid Profile	
Total cholesterol	Triglycerides
High density lipoprotein cholesterol	Low density lipoprotein cholesterol

For continuous clinical laboratory analytes, the absolute value and change from baseline will be summarized by analyte and visit using descriptive statistics for the Safety Population.

Shifts to values outside of the normal range will be presented by analyte and visit and will be summarized by the number and percentage of subjects with evaluable shifts. The denominators for calculating the percentages will be the number of subjects in the Safety Population with both the Baseline value and the value at the specified visit recorded.

If the value is below the lower limit of quantification, then half the lower limit of quantification will be used in the summary tables to calculate the descriptive statistics. If the value is above the upper limit of quantification, then the upper limit of quantification will be used in the summary tables to calculate the descriptive statistics. In the listings, values will be listed as collected without the imputation applied.

All clinical laboratory values, abnormal clinical laboratory values, and clinical significant laboratory values will also be provided in data listings in the Safety Population including data collected at any unscheduled assessments.

Chlamydia and gonorrhea test results will be listed.

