9.4.4.1 Instructions for starting the first pack of tablets

- Women who did not use any contraceptive method or who used a barrier contraceptive method will be instructed to begin the investigational product on the first day of the next menstrual bleeding. Starting on Days 2-5 is also allowed, but a condom must be used until the subject has completed 7 days of uninterrupted active tablet intake. If the menstrual cycle prior to start of first pack of tablets is shorter than 21 days or longer than 35 days, the subject should not start the investigational product and will be withdrawn from the study (section 13.4). The subject should contact the study staff as soon as possible to schedule an Early Termination Visit (section 9.5.4) and to discuss an alternative contraception to use (section 9.6.4.9).
- Women switching from another COC or progestin-only pill will start the investigational product at the time when the next pill pack of the previous pill would have been due.
- Women switching from a hormonal vaginal ring or transdermal patch will start the investigational product when the next application would have been due.

Amendment Final Version 1.1

• Women switching from an injectable hormonal method of contraception will start the investigational product on the first day of spontaneous menstrual bleeding following an interval after the last injection, which can vary depending of the form:

EST*w***TRA**

- 10 months after the injection of a product with a 3-month duration;
- 6 months after the injection of a product with a 2-month duration;
- 3 months after the injection of a product with a 1-month duration.

Starting on Days 2-5 is also allowed, but a condom must be used until the subject has completed 7 days of uninterrupted active tablet intake.

• Women switching from an intrauterine or dermally implantable contraceptive will start the investigational product on the day of removal. A condom must be used until the subject has completed 7 days of uninterrupted active tablet intake.

The first day of the first pink tablet intake after enrollment is Day 1. The subject places one of the 7 self-adhesive day label strips that corresponds to her Day 1 starting day onto the card of the blister to indicate the day she started. The study staff will show the subject how to fix the first label.

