4.3 Predetermined Subgroups

The key subgroup in this study is subjects aged 16 to 35 years, inclusive, at the time of screening. This subgroup is used for the primary efficacy population. All data regarding disposition, baseline characteristics, compliance, exposure and contraceptive efficacy will be presented for subjects aged 16 to 35 years and for all subjects within the specified analysis population.

In addition, subgroup analyses will be performed for the Pearl Index and bleeding data (specifically unscheduled bleeding and spotting and the absence of scheduled bleeding) for the following categories:

- Body Mass Index (BMI) categories (< 30, ≥ 30 kg/m²) at Baseline
- Race category (White, Black or African American, Asian, American Indian or Alaska Native, Native Hawaiian or other Pacific Islander, Other Race)
- Starters (including true new users)/Switchers (see Section 5.5)

- Smokers/Non-smokers at Baseline
- Age (\geq 16 to \leq 25; > 25 to \leq 35 and > 35 years old) at Screening

The non-smokers group includes subjects who are former smokers and never smokers. The smokers group includes subjects who are current smokers. The other race group includes subjects who selected more than one race or whose race was recorded as other race on the CRF.

Quality of life data will be presented for all subjects and for starters and switchers separately.

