5.2 Baseline and Change from Baseline

The Baseline value for each assessment is defined as the last measurement taken prior to first administration of study medication, unless otherwise stated. When the date of the assessment is on the date of first administration, it will be assumed that the assessment was performed prior to first dose. The Baseline value for the Menstrual Distress Questionnaire will be the value collected at Visit 3 because the date of completion is not collected in eCRF for this questionnaire.

For any parameter at a specific visit, change from Baseline is calculated as the value of that parameter at that visit minus the Baseline value of that parameter, as defined above.

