5.5 Switchers, Starters and True New Users

Starters are defined as subjects who have not used hormonal contraceptives within the 3 months prior to the date of first dose of study medication.

Switchers are defined as subjects who have used hormonal contraceptives within the 3 months prior to the date of first dose of study medication.

True new users are defined as subjects who have never received a hormonal contraceptive. This group of subjects is a subset of the group of subjects classed as starters.

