9.6.4 Vital Signs

Unscheduled vital signs assessments will be excluded from the tables.

Vital sign measurements (systolic blood pressure, diastolic blood pressure and heart rate) for the Safety Population will be summarized using descriptive statistics by visit. The change from Baseline will also be summarized in the same manner.

Weight and BMI measurements for the Safety Population will be summarized using descriptive statistics by visit. The change from Baseline will also be summarized in the same manner. BMI will be derived programmatically from the height and weight collected.

All vital signs, weight and BMI measurements will be listed in the Safety Population including data collected at any unscheduled assessments.

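### Laboratory, vital-sign and weight changes are tabulated only pooled, although switchers' baselines are generally taken on, or shortly after, another hormonal method

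*SAP*

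**What the plan says.** SAP 5.2 sets one rule for every safety measure: "The Baseline value for each assessment is defined as the last measurement taken prior to first administration of study medication, unless otherwise stated". It does not require the value to be free of hormonal contraception.

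Protocol 9.4.4.1 fixes how women enter from another method. Those on a combined or progestin-only pill "will start the investigational product at the time when the next pill pack of the previous pill would have been due". For the ring and patch, "Women switching from a hormonal vaginal ring or transdermal patch will start the investigational product when the next application would have been due". Users of an intrauterine or implanted method start on the day of removal. Only injectables carry a required interval (exclusion criterion 36: 300, 180 or 90 days before screening, by product duration). Hormonal users are admitted at screening, since the cycle-length exclusion applies only to non-users.

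For continuous laboratory analytes, SAP 9.6.3 states that "the absolute value and change from baseline will be summarized by analyte and visit using descriptive statistics for the Safety Population"; shifts out of the normal range are likewise tabulated over that whole population. SAP 9.6.4 does the same for blood pressure, heart rate, weight and BMI: "The change from Baseline will also be summarized in the same manner". SAP 6.3 confirms that safety is shown for all subjects together. Protocol 12.5.3, 12.5.6 and 12.5.7 are also pooled.

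The variable that separates the groups already exists. SAP 5.5: "Switchers are defined as subjects who have used hormonal contraceptives within the 3 months prior to the date of first dose of study medication". SAP 4.3 uses it for the Pearl Index and bleeding, and adds: "Quality of life data will be presented for all subjects and for starters and switchers separately". No safety table uses it.

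**The concern.** With one arm and no concurrent control, within-subject change is the main quantitative description of any metabolic, blood-pressure or weight effect. That change means different things in the two groups. For a starter it describes moving from no recent hormonal method to E4/DRSP. For a switcher whose baseline was taken on her previous method, it describes replacing one contraceptive with another. A single mean over both answers neither question, and its value depends on who happened to enrol.

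The protocol gives a reason to expect a difference. Section 7.1 calls ethinylestradiol the most used estrogen in combined pills, and attributes to it a strong effect on liver synthesis, water retention and weight increase. Section 7.2 reports little or no hepatic effect for E4/DRSP, triglycerides included, in a phase 2 study of 5 or 10 mg E4. A woman leaving an ethinylestradiol pill and a woman starting from nothing could therefore change by different amounts.

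**Working it through.** **Step 1: when each measure is taken** (Protocol 9.6.3.3, 9.6.3.5, 9.6.3.7 and Appendix 1).

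| Measure | Scheduled pre-dose | On treatment | After last tablet |
|---|---|---|---|
| Glucose, HbA1c, lipids, LDH, renal function, electrolytes | Visit 1 | Visit 5 | Visit 7 |
| Haematology, liver enzymes, bilirubin, albumin, total protein | Visit 1 | none | Visit 7 |
| Blood pressure, heart rate | Visits 1 and 2 | Visits 3–6 | Visit 7 |
| Weight, BMI | Visit 1 | Visits 4 and 5 | Visit 7 |

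Visit 1 lies up to 45 days before Visit 2 (Protocol 9.5.1). A woman who stays on her method until study drug is due, as the start instructions allow, therefore has laboratory and weight baselines taken on that method. Her blood-pressure baseline, normally Visit 2, is taken on it or shortly after it.

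**Step 2: what the pooled mean estimates.** Define:
- D: mean change from no recent hormonal use to E4/DRSP.
- B: average contribution of the previous method to switchers' baselines (zero for any who had already stopped and returned to their own level).
- p: switcher share of the Safety Population.

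Assume that, apart from the previous method, the groups would respond alike. Starters change by D and switchers by D − B, so

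pooled change = (1 − p)·D + p·(D − B) = D − p·B.

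The distortion is p·B and does not shrink with sample size.

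**Step 3: range.** The plan states no figure to reproduce, and gives neither p nor B. The values below are assumptions. Entries are the pooled change divided by D, that is 1 − p·(B/D).

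| p | B = 0.25D | B = 0.5D | B = D | B = 1.5D |
|---|---|---|---|---|
| 0.10 | 0.975 | 0.95 | 0.90 | 0.85 |
| 0.25 | 0.9375 | 0.875 | 0.75 | 0.625 |
| 0.50 | 0.875 | 0.75 | 0.50 | 0.25 |
| 0.75 | 0.8125 | 0.625 | 0.25 | −0.125 |

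If the previous method acted in the opposite direction, the pooled figure is exaggerated: B = −0.5D and p = 0.50 give 1 + 0.50 × 0.5 = 1.25. If D is near zero, ratios to D mean little and the pooled change is simply −p·B, a change that starters would not show.

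**Step 4: what Visit 7 can show.** Visit 7 falls in Cycle 14, Days 16–23 (Protocol 9.5.3.5). Day k of Cycle 14 is k days after a last tablet taken on Cycle 13 Day 28, so Visit 7 is 16–23 days after the last tablet. The Early Termination Visit has the same window. Protocol 9.4.7 has the next contraceptive begin by the day after the last tablet. Visit 7 values are therefore off study drug, possibly on another method, and D − p·B does not describe them.

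**The case against.** The facts of timing and pooling are not in dispute. The case on the other side concerns what follows from them, and much of it stands.

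- **Nothing is tested.** SAP 9.0 plans no formal statistical analyses, and the SAP follows the protocol. The pooled table correctly describes what it claims to describe.
- **Safety rests mainly on adverse events.** SAP 4.2.2 frames the safety variable that way, and clinically significant laboratory and vital-sign findings are recorded as adverse events. A reader might infer that the general-safety objective goes unanswered; the documents do not support that.
- **Shifts remain partly readable.** A reader might infer that shift tables are uninterpretable because switchers may already be abnormal at baseline. Clinically relevant abnormal screening results, blood pressure at or above 140/90 mmHg, treated dyslipoproteinemia and hyperkalemia are all excluded, and absolute values by visit are also shown. Some out-of-range baselines judged not clinically relevant can remain.
- **Switchers are heterogeneous.** The three-month definition includes women who stopped before their baseline sample, and it mixes estrogen-containing, progestin-only and intrauterine methods. There is no single B.
- **Starters are not a clean estimate either.** Regression to the mean, and attrition with an assumed dropout of about 45% (Protocol 12.1), remain.
- **Nothing is lost.** Individual values and contraceptive use are listed, so the split could be made later.

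The last point does not remove the case for prespecification: a table planned now reads differently from one assembled after the pooled result is known.

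**Conclusion.** The point holds as a limit on interpretation. Switchers' baselines generally reflect a previous hormonal method, and no planned safety table separates them from starters, so the pooled change mixes two contrasts. In the assumed grid the pooled change lies between 0.975 and −0.125 of D, and above D if the previous method acted the other way. Those figures illustrate sensitivity; they do not estimate what will be seen.

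Two stronger readings are tempting. One is that the previous method carries over into on-treatment values. The documents show only that it may be present in the baseline value; nothing indicates persistence into later cycles. The other is that pooling is known to hide or reverse an effect. That would need p and B, which are absent. The protocol's remarks on ethinylestradiol suggest a direction for some measures at most: of the hepatic and hemostatic markers listed in Protocol 7.2, only triglycerides appears in SAP Table 4, and Section 7.1 gives no figures for blood pressure, heart rate, haematology or electrolytes.

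**What to change.** In SAP 9.6.3 and 9.6.4, present absolute values, change from baseline and (for laboratory data) shifts for starters and for switchers as defined in SAP 5.5, alongside the overall column. SAP 9.7.1 already does this for quality of life.

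Base interpretation on the on-treatment visits: Visit 5 for glucose, HbA1c, lipids, LDH, renal function and electrolytes; Visits 3–6 for blood pressure and heart rate; Visits 4 and 5 for weight and BMI.

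Add a footnote with three statements:
- The starter column is the cleaner description of change from no recent hormonal use.
- Switchers are a mix of previous methods, and some had stopped before baseline.
- Visit 7 values are taken 16–23 days after the last tablet, possibly on another contraceptive, and do not show an on-drug effect in either group. The split does not cure this, and haematology and the liver panel have no other scheduled post-baseline sample.

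The cost is extra tables from a variable already derived; no new data and no change to conduct are needed. A change in starters may look larger than the pooled figure, and the text should be ready to explain that.

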9.6.4 Vital Signs

Unscheduled vital signs assessments will be excluded from the tables.

Vital sign measurements (systolic blood pressure, diastolic blood pressure and heart rate) for the Safety Population will be summarized using descriptive statistics by visit. The change from Baseline will also be summarized in the same manner.

Weight and BMI measurements for the Safety Population will be summarized using descriptive statistics by visit. The change from Baseline will also be summarized in the same manner. BMI will be derived programmatically from the height and weight collected.

All vital signs, weight and BMI measurements will be listed in the Safety Population including data collected at any unscheduled assessments.

9.6.5 Physical and Gynecological Examinations

Physical and gynecological examination assessments will be summarized for the Safety population by visit. For each body system and assessment category, the number and percentage of subjects will be presented. The denominators for calculating the percentages will be based on the number of subjects evaluated for a particular body system. Unscheduled physical examinations will not be summarized.

All physical and gynecological examination data will be listed in the Safety Population.

9.7 Other Secondary Endpoints (Excluding PK)

9.7.1 Quality of Life

Quality of life data will be summarized in the ITT Population. Summaries will be provided overall and by switchers and starters separately.

For the Q-LES-Q-SF, the absolute values and change from baseline of the percentage maximum, how satisfied have you been with your medication and how would you rate your overall life satisfaction and contentment during the past week will be summarized descriptively by visit.

For the Menstrual Distress Questionnaire, the absolute values and change from baseline for the scores for pain, water retention, autonomic reactions, negative affect, impaired concentration, behaviour change, arousal and control will be summarized descriptively by visit and by phase. The phases are menstrual (most recent flow), premenstrual (four days before) and intermenstrual (remainder of cycle).

All quality of life data will be listed in the ITT Population.

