9.6.4.11 Subjects' well-being

Subjects' well-being will be evaluated using two well-established questionnaires: the Quality of Life Enjoyment and Satisfaction Questionnaire – Short Form and the Menstrual Distress Questionnaire.

The baseline questionnaires will be given to the subject at Visit 2. The subject will be instructed to fill them in at home on or before the first day of study medication intake (Day 1). At the next visit, the study site personnel will ensure for the questionnaire completion.

The end-of-treatment questionnaires will be given to the subject at Visit 6. The subject will be instructed to fill them in at home between Day 7 and Day 14 of the 13th treatment cycle. At the next visit, the study site personnel will ensure for the questionnaire completion.

In case of premature study discontinuation, the subjects will be asked to fill in the questionnaires during the Early Termination Visit.

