12.6.7 Quality of Life

The total score of the Quality of Life Enjoyment and Satisfaction Questionnaire Short Form (Q-LES-Q-SF) (Appendix 4) will be derived by summing the first 14 items to obtain the raw total score, which is then transformed into a percentage maximum using the following formula: (raw score -14)/56. The absolute values and change from baseline of the percentage maximum, how satisfied the subject has been with the medication and how would the subject rate the overall life satisfaction and contentment during the past week will be summarized descriptively by visit.

The Menstrual Distress Questionnaire will be scored according to the manual (Appendix 5)¹⁰. The absolute values and change from baseline for the scores for pain, water retention, autonomic reactions, negative affect, impaired concentration, behavior change, arousal and control will be summarized descriptively by visit. Summaries will be provided overall and by switchers and starters separately.

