Appendix 4. Quality of Life Enjoyment and Satisfaction Questionnaire – Short Form (Q-LES-Q-SF)

Taking everything into consideration, during the past week how satisfied have you been with your.....

	Very Poor	Poor	Fair	Good	Very Good
physical health?	1	2	3	4	5
mood?	1	2	3	4	5
work?	1	2	3	4	5
household activities?	1	2	3	4	5
social relationships?	1	2	3	4	5
family relationships?	1	2	3	4	5
leisure time activities?	1	2	3	4	5
ability to function in daily life?	1	2	3	4	5
sexual drive, interest and/or performance?*	1	2	3	4	5
economic status?	1	2	3	4	5
living/housing situation?*	1	2	3	4	5
ability to get around physically without feeling dizzy or unsteady or falling?*	1	2	3	4	5
your vision in terms of ability to do work or hobbies?*	1	2	3	4	5
overall sense of well being?	1	2	3	4	5
medication? (If not taking any, check here and leave item blank.)	1	2	3	4	5
How would you rate your overall life satisfaction and contentment during the past week?	1	2	3	4	5

*If satisfaction is very poor, poor or fair on these items, please UNDERLINE the factor(s) associated with a lack of satisfaction.

Amendment Final Version 1.1

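### The planned change from baseline for the Q-LES-Q-SF medication item subtracts ratings of different medicines in a selected subset, so overall and for starters it cannot be read as an effect of the study drug.

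*SAP*

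**What the plan says.** SAP 9.7.1 summarises, in the ITT population, "the absolute values and change from baseline of the percentage maximum, how satisfied have you been with your medication", plus the overall life satisfaction item. It does so by visit, overall and separately for switchers and starters. Protocol 12.6.7 plans the same change for "how satisfied the subject has been with the medication". SAP 4.2.2 lists change to end of treatment in the different questionnaire items among the other secondary variables. The matching objective in SAP 2.3 is the impact of the study drug on functioning and well-being.

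The form is in protocol Appendix 4. Its stem is "Taking everything into consideration, during the past week how satisfied have you been with your", and the fifteenth line reads "medication? (If not taking any, check here and leave item blank". The item names neither the study pill nor contraception.

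The timing is in protocol 9.6.4.11. Women are to "fill them in at home on or before the first day of study medication intake (Day 1"). The end-of-treatment form is filled in "between Day 7 and Day 14 of the 13th treatment cycle", or at the Early Termination Visit for women who leave early. SAP 5.2 states: "The Baseline value for each assessment is defined as the last measurement taken prior to first administration of study medication". It also assumes that an assessment dated on the day of first dose came before that dose.

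**The concern.** A change from baseline is meaningful when the same thing is rated twice. Here the question stays the same but the medicine it refers to changes. Before the first tablet a woman can rate only a previous contraceptive or some unrelated medicine, and if she takes nothing she is told not to answer. In Cycle 13 the study pill is among the medicines she rates.

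Two consequences follow. The difference mixes a change of medicine with any change in satisfaction. It also exists only for women who took some medicine at baseline, a selected part of the ITT population. The result would stand in a change-from-baseline column, under an objective about the impact of the study drug, beside two other scores (the percentage maximum and overall life satisfaction) that do have the same referent at both times.

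**Working it through.** This point turns on what the item refers to at each time, so most of the check is a side-by-side reading.

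**1. Is the item inside the total score?** SAP 5.12 sums the first 14 items and divides (raw score − 14) by 56. Fourteen items scored 1 to 5 range from 14 × 1 = 14 to 14 × 5 = 70, a width of 70 − 14 = 56, which reproduces the plan's divisor. Fifteen items would need 15 × 4 = 60. The medication item is therefore outside the total, and the percentage maximum is unaffected.

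**2. What does each answer refer to?**

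| Group | Baseline answer (pre-dose, past week) | End-of-treatment answer (past week) | What the change compares |
|---|---|---|---|
| Starters on no medicine | Blank by instruction | Study pill, if still taking it | Undefined |
| Starters on some medicine | A medicine other than a hormonal contraceptive | Study pill and any other medicine | Different medicines |
| Switchers | Previous contraceptive, another medicine, or both | Study pill and any other medicine | At best, previous against study medication |
| Early leavers | As above | Whatever was taken after stopping, or blank | May not involve the study pill |

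- The starter rows follow from SAP 5.5: starters used no hormonal contraceptive in the 3 months before first dose.
- The switcher row is limited by the same section. Use at any time within 3 months makes a woman a switcher, so her past week need not include a contraceptive. Under protocol 9.4.4.1, however, women coming from another combined pill start when their next pack would have been due, so many can rate the old method.
- The early-leaver row follows from protocol 9.5.4. The visit falls 16 to 23 days after the last tablet, beyond the item's one-week recall, and sites may supply another contraceptive beforehand.

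**3. Is the blank handled?** The missing-item rule in SAP 5.12 covers only the percentage maximum. Nothing is stated for a blank on this single item.

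**4. How many women?** The documents do not give the share, q, with no baseline answer. With N = 2,000 women, at most N × (1 − q) can have a change score. As pure assumption:

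- q = 25%: 2,000 × 0.75 = 1,500
- q = 50%: 2,000 × 0.50 = 1,000
- q = 75%: 2,000 × 0.25 = 500

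The width of this range shows only that the share must be counted from the data.

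**5. How many final answers could be off drug?** Protocol 12.1 assumes about 45% dropout among the 1,800 women aged 16 to 35: 1,800 × 0.45 = 810 early leavers and 1,800 − 810 = 990 completers. Some of the 810 will be lost to follow-up and give no answer. Those who do answer would do so mostly after stopping.

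**The case against.** The strongest reply is that little is lost. SAP 9.7.1 already summarises absolute values by visit, so a woman with a blank baseline still contributes her final rating. SAP 9.0 shows the number of subjects with each continuous summary, so a smaller n for the change would be visible. Switchers are reported separately, and for many of them old method against study pill is a readable contrast. No formal analysis is planned, and protocol 9.6.4.10 assesses acceptability through discontinuation rates and reasons, not through this item.

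All of that stands, and it keeps the point small. It does not rescue the overall and starter change scores. A visible n does not say which women are missing or which medicine was rated, and the starter split isolates exactly the group in which the baseline answer cannot concern a recent hormonal contraceptive.

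Three stronger readings are tempting and are not supported:

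- **A particular large share of the cohort drops out of the change.** The documents give no figure for women on no medicine at baseline.
- **Everyone with a blank baseline could still give an interpretable final rating.** Early leavers normally answer 16 to 23 days after the last tablet, so their rating may not concern the study pill.
- **The plan presents this change as satisfaction with the trial treatment.** It does not say so. The stated objective is functioning and well-being, and the table shells are not in the documents.

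**Conclusion.** The point holds, with minor impact. By the plan's own definitions, the baseline answer to this item precedes study dosing and concerns another medicine, or is blank by instruction. The overall and starter change scores have no coherent meaning as an effect of the study drug. The switcher change can be read only as previous medication, not necessarily a contraceptive, against medication at end of treatment.

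The effect is confined to one descriptive item outside the 14-item score. The Pearl Index, the percentage maximum and the overall life satisfaction item are untouched. The conclusion rests on women following the printed instruction to leave the item blank, and on baseline forms being completed before the first tablet, as SAP 5.2 assumes. It does not depend on any assumed share of women without medication.

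**What to change.** In SAP 9.7.1, noting the departure from protocol 12.6.7 and from the item-level change variable in SAP 4.2.2:

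- Drop the change from baseline for the medication item overall and for starters.
- Report the distribution of its five response categories at end of treatment, with the number blank at each visit.
- Show women who answered in Cycle 13 while on study drug separately from early leavers who answered at the Early Termination Visit after stopping.
- If a switcher change is kept, label it as previous medication (not necessarily a contraceptive) against medication at end of treatment.
- Leave the percentage maximum and the overall life satisfaction item as they are.

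No new data are needed. The cost is an edit to SAP 9.7.1 that records the departure, and one changed table shell. The downside is that one descriptive summary of a stated secondary variable becomes narrower.
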